## **1.5. Description of and justification for the route of administration, dosage, dosing regimen, and treatment period**

### **1.5.1 Description and justification of the study design**

This is an international multicenter double-blind randomized study to compare the efficacy and safety of two dosing regimens of BCD-085 (JSC BIOCADC, Russia) in patients with moderate to severe plaque psoriasis in 3 parallel arms [Arm 1: BCD-085 120 mg Q2W after induction; Arm 2: BCD-085 Q4W after induction; Arm 3: placebo (until Week 10), blinded therapy]. At Week 12, the therapy will be unblinded, and the efficacy will be assessed. Starting from Week 14, patients in Arm 1 will receive BCD-085 Q4W through Week 50. Starting from Week 14, patients in Arm 2 will continue to receive BCD-085 Q4W through Week 50. Patients from Arm 3 will receive BCD-085 at Weeks 12, 13 and 14, then Q4W (from Week 18 through Week 50). To assess long-term efficacy and safety of BCD-085, and to evaluate maintenance of the stable treatment effect with no increased safety risk after 1-year treatment, the treatment in  $\geq$ PASI 75 responders at Week 52 will be continued Q4W starting from Week 54 through Week 154 (in patients from Arms 1 and 2) or through Week 166 (in patients from Arm 3).

Since the planned population size is 213 patients with moderate to severe plaque psoriasis, it is unlikely that all of them can be recruited at one study site. To ensure optimal timing, patients will be recruited at several sites.

In this study, the effects of BCD-085 will be compared with the effects of placebo to make adequate and objective conclusions on the efficacy and safety of BCD-085. The necessity of using placebo in the development of systemic medications is also mentioned in the EMA's guidelines on clinical investigation of medicinal products for the treatment of psoriasis [CHMP/EWP/2454/02 corr, 2004].

The double-blind design is used to minimize the bias during the physician's and patient's assessment of treatment results, minimize systemic errors, and, therefore, to improve the validity of study results.

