### 9.3.1. Non-inferiority hypothesis

The sample size required to run the study was calculated on the basis of the literature data on clinical efficacy. During study planning, the hypothesis stating that BCD-085 Q4W is non-inferior to BCD-085 Q2W ( $H_0: \varepsilon \leq \delta$ ,  $H_1: \varepsilon > \delta$ , where  $\varepsilon$  is true difference in the frequency of the efficacy variable between the arms,  $\delta$  is non-inferiority margin) was tested with the following error values: type I error of 5% ( $\alpha=0.05$ ), type II error of 20% ( $\beta=0.2$ ), power of test of 80%. The

Translated from Russian to English, dated 26-Nov-2019

efficacy endpoint used to calculate the sample size was PASI 75 rate by Week 12 in each arm [REDACTED]

1. Efficacy variable in the arms: BCD-085 every 2 weeks ( $p_{2w}$ ) and BCD-085 every 4 weeks

( $p_{4w}$ ):

$p_{2w} = 0.891$  (89.1%)

$p_{4w} = 0.826$  (82.6%)

2. The true difference in the rates of the efficacy parameter between two regimens of BCD-085:

$$\varepsilon = p_{4w} - p_{2w} = 0.826 - 0.891 = (-0.065) (6.5\%)$$

3.  $z_{1-\alpha}$  and  $z_{1-\beta}$  – quantiles of normal distribution  $N(0,1)$  (mean: 0, standard deviation: 1).

4.  $k$  – coefficient for ratio between sample sizes [BCD-085 Q2W ( $n_{2w}$ ) to BCD-085 Q4W ( $n_{4w}$ )]:

$$n_{2w}/n_{4w} = k.$$

5. The non-inferiority margin for BCD-085 once every 4 weeks vs. BCD-085 once 2 weeks was considered to be the following:

$$\delta = (-0.2038) (-20.38\%)$$

[REDACTED]

[REDACTED]

[REDACTED]

[REDACTED]

[REDACTED]

[REDACTED]

[REDACTED]

[REDACTED]

[REDACTED]

After that, in accordance with the method described in [Chow Sh.-Ch., Shao J., Wang H., 2008], sample size was calculated using the assumption that sample sizes of the BCD Q4W ( $n_{4w}$ ) arm and the BCD Q2W ( $n_{2w}$ ) arm are the same, i.e.  $k = 1$ .

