#### **9.4. Suitable significance level**

The level of significance was set as 0.05 (5%) with the statistical power of 0.8 (80%).

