- **Arm 2:** Patients in this arm (85 subjects) will receive BCD-085 120 mg (two subcutaneous injections, 60 mg in 1.0 mL each) once a week during the first 3 weeks (induction) and then once every 4 weeks through Week 10. Thus, the investigational product will be administered on Day 1 of Week 0, Week 1, Week 2, Week 6 and Week 10. To maintain the study blind, patients of this arm will receive placebo (2 injections) on Day 1 of Week 4 and Week 8.
- **Arm 3:** Patients of this arm (43 subjects) will receive placebo (2 subcutaneous injections of placebo, 1.0 mL each) on Day 1 of Week 0, Week 1, Week 2, Week 4, Week 6, Week 8 and Week 10.

On Week 12, the treatment efficacy will be assessed with a PASI 75 score, and the treatment will be **unblinded**. Patients from Arms 1 and 2 will be given BCD-085 once every 4 weeks. Patients from Arm 3 will receive BCD-085 as follows:

- ✓ Induction: Weeks 12, 13, and 14, once a week;
- ✓ Weeks 18 through 50: once every 4 weeks.

Therefore, there will be 3 arms even after unblinding, and patients will receive BCD-085 according to the regimens described below:

- a) Patients in Arm 1 will receive BCD-085 120 mg (2 subcutaneous injections of 60 mg each) once every 4 weeks starting from Week 14 through Week 50.
- b) Patients in Arm 2 will receive BCD-085 120 mg (2 subcutaneous injections of 60 mg each) once every 4 weeks starting from Week 14 through Week 50.

c) Patients in Arm 3 will receive BCD-085 120 mg once a week at Weeks 12, 13, 14, then once every 4 weeks (Weeks 18, 22, 26, 30, 34, 38, 42, 46, 50).

Extension study period (from Week 54 through Week 154 for Arms 1 and 2, through Week 166 for Arm 3):

During **the extension study period** all patients who achieved PASI 75 at Week 52 will receive BCD-085 120 mg once every 4 weeks:

- a) Patients from Arm 1 will receive BCD-085 from Week 54 through Week 154.
- b) Patients from Arm 2 will receive BCD-085 from Week 54 through Week 154.
- c) Patients from Arm 3 will receive BCD-085 from Week 54 through Week 166.

Patients who failed to achieve PASI 75 at Week 52 will be withdrawn from the study.

In Arm 3, treatment will be extended by 12 weeks so that the total treatment duration in all arms can be 154 weeks. During the main treatment period (during the first 12 weeks of the study), patients from Arm 3 receive placebo, so the treatment period for these patients is extended to 166 weeks.

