4. EVALUATION CRITERIA

4.1 Efficacy endpoints

Primary endpoint

- Proportion of patients who achieved PASI 75 at Week 12, by study arms.

Secondary endpoints in the main treatment period (Week 0 to Week 54):

- Proportion of patients who achieved PASI 75/90/100 at Weeks 8, 16, 24, 42 and 52, by study arms.
- Proportion of patients with sPGA score 0 or 1 at Weeks 8, 12, 16, 24, 42, and 52.
- Proportion of patients with sPGA score 0 at Weeks 16, 24, 42, and 52.
- Relative change from baseline in PASI score at Weeks 8, 12, 16, 24, 42 and 52.
- Change from baseline in itch severity measured with visual analog scale (VAS) (0 mm to 100 mm) at Weeks 1, 12, 24, and 52.
- Change from baseline in Nail Psoriasis Severity Index (NAPSI) score at Week 12, 24, and 52.
- Change from baseline in Dermatology Life Quality Index (DLQI) score at Weeks 8, 12, 24, 42, and 52.
- Proportion of patients with DLQI score 0 or 1 at Weeks 24, 42, and 52.

- Proportion of patients (among those with psoriatic arthritis) who achieved an ACR20/50/70 at Weeks 12, 24, and 52.

Secondary endpoints during the extension study period (Week 54 through Week 166):

- Proportion of patients who maintained PASI 75/90/100 response after 62, 74, 86, 98, 110, 122, 134, 146, and 154 weeks of treatment vs. response after 52 weeks of treatment with BCD-085.
- Proportion of patients who maintained sPGA 0-1 response after 62, 74, 86, 98, 110, 122, 134, 146, and 154 weeks of treatment vs. response after 52 weeks of treatment with BCD-085.
- Proportion of patients who maintained sPGA score 0 response after 62, 74, 86, 98, 110, 122, 134, 146, and 154 weeks of treatment vs. response after 52 weeks of treatment with BCD-085.
- Proportion of patients who maintained DLQI score 0-1 after 62, 74, 86, 98, 110, 122, 134, 146, and 154 weeks of treatment vs. response after 52 weeks of treatment with BCD-085.
- Time to loss of PASI 75/90/100, sPGA 0-1/sPGA 0, DLQI 0-1 response during the treatment with BCD-085.
- Proportion of patients who maintained ACR 20/50/70 response (among patients with psoriatic arthritis) after 62, 74, 86, 98, 110, 122, 134, 146, and 154 weeks of treatment vs. response after 52 weeks of treatment with BCD-085.
- Proportion of patients who achieved PASI 75/90/100 response after 62, 74, 86, 98, 110, 122, 134, 146, and 154 weeks of treatment with BCD-085.
- Proportion of patients with sPGA score 0 or 1 after 62, 74, 86, 98, 110, 122, 134, 146, and 154 weeks of the treatment with BCD-085.

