8.2. Description of the Statistical Methods to be Employed

The statistical analysis will be performed using two-sided hypothesis tests. The statistical significance level is 0.05.

The study hypothesis of non-inferior efficacy of BCD-085 once every 4 weeks vs. BCD-085 once every 2 weeks will be proved by comparing the lower bound of the 95% confidence interval for the difference in proportions of patients with PASI 75 at Week 12 between the BCD-085 Q4W and BCD-085 Q2W with pre-specified non-inferiority margin (δ) equal to -20.38%.

The hypothesis stating the superior efficacy of BCD-085 over placebo will be proved by comparing the lower bound of the 95% confidence interval for the difference in proportions of patients with PASI 75 by Week 12, in each BCD-085 arm and placebo arm, with pre-specified non-inferiority margin (δ , 0%).

Quantitative Data

The following quantitative data will be analyzed in the study:

Efficacy:

- Relative PASI change,
- Change in itch severity (VAS, 0 to 100 mm),
- Change in NAPSI score,
- Change in quality of life according to the DLQI score,

- Time to loss of PASI 75/90/100, sPGA 0-1/sPGA 0, DLQI 0-1 response during the treatment with BCD-085,

Safety:

- CBC results,
- Blood chemistry results,
- Vital signs,

Demographics and other baseline characteristics:

- General information (age, body weight, height, BMI),
- Duration of the disease, severity and the area of psoriasis (PASI), BSA, severity by sPGA, severity of nail psoriasis (NAPSI), severity of pruritus (VAS), quality of life score (DLQI), the presence of depression (Beck's score), functional activity (HAQ-DI), tender joint count (of 68), swollen joint count (of 66).

Quantitative data will be described using the following descriptive statistics: mean, SD, median, quartiles, CV, min, and max.

Quantitative variables will be tested for normality using the Shapiro-Wilk test.

Normally distributed quantitative variables will be tested using the two-sample Student's t-test, Welch's t-test, and ANOVA.

Non-normally distributed quantitative variables will be tested using the Mann-Whitney U-test, the Wilcoxon test, the Kruskal-Wallis test, and the Friedman test.

Time to loss of response will be assessed using log-rank test, Kaplan-Meier curves, and Cox regression model. Time will be counted from the response during the treatment with BCD-085. Right censoring can be used to analyze time to events.

Categorical Data

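### Extension-period 'achieved' response rates can be computed only in Week 52 PASI 75 responders and so overstate long-term response; the origin and risk set for time to loss are undefined

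*SAP*

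**What the plan says.** - **Entry rule.** SAP 3.1, as in the Protocol synopsis and section 4.2: "Patients who failed to achieve PASI 75 at Week 52 will be withdrawn from the study". From Week 54 only Week 52 PASI 75 responders are treated and assessed.
- **Endpoints.** SAP 4.1 has a list headed "Secondary endpoints during the extension study period (Week 54 through Week 166". It contains three kinds of response endpoint: proportions who 'maintained' a response, anchored to the response after 52 treatment weeks; proportions who 'achieved' a response at treatment Weeks 62 to 154, with no denominator given; and time to loss of response.
- **Time to loss.** SAP 8.2: "Time will be counted from the response during the treatment with BCD-085". No visit, risk set or event definition is given, and right censoring is optional.
- **Population and missing data.** SAP 7 assesses efficacy in all randomized patients and defines no extension population. SAP 8.4 substitutes no missing data, and there is no non-responder rule.
- **Purpose.** Protocol 1.5.1 gives the reason for continuing treatment: "To assess long-term efficacy and safety of BCD-085, and to evaluate maintenance of the stable treatment effect".

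**The concern.** Patients who fail at Week 52 have no PASI afterwards. With nothing substituted, they drop out of every later 'achieved' proportion, although SAP 7 says they belong in the analysis. The long-term rate then describes patients chosen because they were responding, while its label suggests response under BCD-085 treatment generally. For PASI 75 in Arms 1 and 2 every entrant is a responder at the reference visit, so 'achieved' and 'maintained' become the same number and the first adds nothing.

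Time to loss carries a second, conditional risk. If it were analysed only in entrants and timed from a response before Week 52, the time up to Week 52 would be nearly event-free by selection. It would be only nearly so, because the rule looks at one visit and a patient can lose response and regain it.

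Maintenance of response is the first extension objective, and Supplementary Reports 2 and 3 will carry these figures. If the denominator and time origin stay open, they can be chosen after open-label data have been seen.

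**Working it through.** The plan states no figure for this point, and no Week 52 or extension rates for this trial, so the inputs below are assumed ranges.

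**1. 'Achieved' denominator.** Let r be the proportion with PASI 75 at Week 52 and m the proportion of entrants responding at a later visit. The entrants-only rate is m. With Week 52 withdrawals counted as non-responders, the rate among those who started is r × m. The overstatement is m(1 − r). Other dropout is ignored.

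Values of r: 98% is close to the one-year PASI 75 of 98.06% in the Phase II psoriasis extension (Protocol 1.3.2.2.2). The values 89.1% and 82.6% are the Week 12 planning rates for Q2W and Q4W (Protocol 9.3.1). The value 75% is an assumed low end.

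| r | Entrants of 85 | Entrants-only rate (m = 0.90) | r × m | Overstatement, points |
|---|---|---|---|---|
| 98% | 83 | 90% | 88.2% | 1.8 |
| 89.1% | 76 | 90% | 80.2% | 9.8 |
| 82.6% | 70 | 90% | 74.3% | 15.7 |
| 75% | 64 | 90% | 67.5% | 22.5 |

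The result depends little on m. For m from 0.85 to 0.95 the four rows become 1.7–1.9, 9.3–10.4, 14.8–16.5 and 21.3–23.8 points.

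**2. Time to loss, entrants only, clock from Week 12.** Assume a constant hazard λ = −ln(1 − L)/52, where L is the annual loss, and loss observed in continuous time. True maintenance 52 weeks after the origin is 1 − L. An entrant has no event in the first 52 − 12 = 40 weeks, so only the last 12 weeks count and apparent maintenance is (1 − L)^(12/52).

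For the loss rate to Week 154, let E = 1 − exp(−102λ), since 154 − 52 = 102. Apparent events per 100 patient-years are 5200 × E / (40 + E/λ). For L = 10%: λ = 0.002026, E = 0.1867, and 5200 × 0.1867/(40 + 92.15) = 7.3.

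| Annual loss L | True maintenance | Apparent | Overstatement, points | True rate per 100 PY | Apparent rate |
|---|---|---|---|---|---|
| 5% | 95% | 98.8% | 3.8 | 5.1 | 3.6 |
| 10% | 90% | 97.6% | 7.6 | 10.5 | 7.3 |
| 20% | 80% | 95.0% | 15.0 | 22.3 | 15.0 |

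A simulation of 400,000 patients gave the same values. Starting the entrants' clock at Week 52 returned 95.0%, 90.1% and 80.1%, so the bias disappears. It also disappears if all responders are analysed from Week 12 with losses before Week 52 counted as events.

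**3. Which reading does the text support?** The 'maintained' endpoints carry an explicit 52-week anchor and time to loss does not. On-treatment PASI is first measured at Week 8. An early origin is therefore possible, but neither it nor a restriction to entrants is written anywhere.

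**The case against.** The strongest reply is that the SAP names all randomized patients and restricts neither analysis to entrants. A patient who responds at Week 8, loses response at Week 42 and fails at Week 52 has PASI recorded at all three visits, and nothing prevents counting that loss. This stands for time to loss. A reader might infer that the SAP starts the clock at an early response among entrants, but it names no visit and no risk set. The reply does not rescue the 'achieved' proportions: withdrawn patients have no later values, and no rule assigns them one.

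The 'maintained' endpoints are openly conditional and sound if labelled so. Week 52 PASI 75 by arm is itself a main-period endpoint due in Supplementary Report 1, so the size of the selection will be visible. If Week 52 response is near 98%, the shift is only about 2 points.

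Three stronger readings are tempting and fail:

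- *That Arm 3 will look more stable because it is selected at 52 − 12 = 40 treatment weeks but anchored at 52 (study Week 64).* The endpoint runs on treatment time. A patient in any arm who loses response between treatment Weeks 40 and 52, and has not regained it, is a non-responder at the reference and is excluded. Anchoring all arms at study Week 52 would instead compare 40 with 52 treatment weeks.
- *That 'achieved' and 'maintained' coincide throughout.* They do so only for PASI 75 among entrants in Arms 1 and 2. For PASI 90/100, sPGA or DLQI an entrant can newly respond after Week 52.
- *That almost all loss would be hidden.* A horizon just past Week 52 gives that impression. A Week 8 origin plus 52 weeks, for example, is study Week 60, where no PASI visit exists. Over follow-up to Week 154 the distortion is about 1.4-fold (10.5/7.3).

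**Conclusion.** The point holds for the 'achieved' proportions. The withdrawal rule together with no substitution produces an observed-case rate among selected responders, which conflicts with the stated population and overstates response among those who started BCD-085. The size runs from about 2 to 22 points as assumed Week 52 PASI 75 falls from 98% to 75%, with 90% of entrants responding later and no other dropout.

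For time to loss the finding is a gap in specification. Bias needs both an origin before Week 52 and an entrants-only risk set. Under both conditions, with a constant hazard and a Week 12 origin, 52-week maintenance reads about 4, 8 or 15 points high for annual loss of 5%, 10% or 20%. An all-responder analysis has no such bias.

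These are secondary endpoints of an open-label period. The Week 12 primary analysis is not touched.

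**What to change.** In SAP 8.2 and 8.4:

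- **'Achieved' endpoints in the extension.** Report the proportion among all patients who received BCD-085, counting those withdrawn under the Week 52 PASI 75 rule as non-responders. Beside it, show the entrants-only figure labelled as conditional on Week 52 response. State separately how responders who decline the extension or leave for other reasons are handled, since Protocol 4.6.1 makes entry depend on consent and the investigator's decision.
- **Time to loss.** Analyse all BCD-085 responders from first response, with losses before Week 52 as events, including in patients withdrawn at Week 52. If an entrants-only analysis is also wanted, start the clock, or use delayed entry, at the Week 52 selection visit. Define the event and the censoring rule.
- **'Maintained' endpoints.** Keep them, labelled as conditional on response after 52 treatment weeks.

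The cost is SAP wording and a few extra tables, and the long-term figures will be less favourable. No new data are needed, and treatment and entry rules stay as they are.

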Any other therapy during the study	Any medications other than the investigational product that are used to perform the study procedures. This includes, for example, the drugs used as part of the combination therapy.
Patient's premature withdrawal (dropout)	The time point when the patient discontinues the study before the planned completion of the study therapy and/or assessments. At this time point, the study therapy stops, and no further assessments are planned (follow-up for survival and/or disease progression may be an exception). If the patient discontinues the study due to an event planned by the Protocol (for example, a complete response), he/she is considered a dropout anyway.
Completion of the study	The time point corresponding to the final patient's visit.
Study therapy	Any medication or a combination of medications used in any arm as part of study procedures, including concomitant medications and introductory therapy before the active medication.
Concomitant therapy	Therapy with any drugs included in the study therapy, except for the test drug and reference drug. For example, drugs used for combination therapy, pre-medication etc.
Discontinuation of study therapy	Time point when the investigational therapy is terminated regardless of what caused the termination. It does not necessarily coincide with patient's withdrawal from the study.
Variable	An identifier used in data analysis; it is obtained directly or indirectly from data gained during the specified assessment within the specified time points.

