### **1.5.3. Justification of placebo use**

Some of the patients in this study will receive placebo. This is necessary to draw unbiased conclusions on the efficacy and safety of the study drug and is a standard approach for investigating systemic medications for psoriasis [15-22]. The necessity of using placebo in this case is also mentioned in the EMA's Guidelines on clinical investigation of medicinal products for the treatment of psoriasis [CHMP/EWP/2454/02 corr, 2004].

Patients involved in this study will not be exposed to excessive risk because of getting a placebo. If the disease worsens and requires additional therapy, the patient can always discontinue the study and receive all the medications he/she needs.

This being said, the use of placebo in one of the arms does not pose any threat to the patients' safety and is in full compliance with the international guidelines and practice of studies of medicinal products for the treatment of psoriasis.

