**5.4.1. Follow-up of patients who received at least one dose of the investigational product**

The following should be done if the patient who received at least one dose of the investigational product discontinues the study early:

- On the day of withdrawal, the Early Withdrawal Visit should be conducted and the investigator should complete the Early Withdrawal Visit and the End of Study forms in the eCRF. The Protocol does not specify the amount of procedures to be performed during the Early Withdrawal Visit; this is to be determined on a case-by-case basis.

Said procedures are mandatory for all subjects who prematurely withdrew from the study, except for the subjects who are lost to follow-up or are physically unable to attend the visit. All records must be supported with appropriate source documents.

If the subject discontinues the study due to an AE/SAE, the investigator should conduct further treatment and follow-up after the Early Withdrawal Visit in accordance with the study site standards for the treatment of a certain AE/SAE. The patient is to be **followed up until the AE or SAE resolves completely**.

If a woman involved in the clinical study or a partner of a clinical study participant becomes pregnant, this does not need to be reported as an AE unless the baby has any congenital abnormality or birth defect (these should be recorded as SAEs). However, all pregnancies must be documented in a Pregnancy Report Form and reported to the Sponsor as soon as possible. Women who discontinued the study because of becoming pregnant during the study should be monitored throughout the entire pregnancy and 6 months after childbirth to evaluate the mother's and child's health. Such monitoring is performed when possible and requires patient's consent for the pregnancy follow-up. Information on pregnancy course and outcome should be recorded in the source documentation (with consent from the patient).

Information about the health of the patient prematurely withdrawn from the study must be recorded in the source documentation and eCRF.

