### **6.2.2. Prohibited concomitant therapy**

Methods and medications prohibited in this study:

- ✓ Biologics (including other anti-IL-17 monoclonal antibodies, TNF $\alpha$  inhibitors, anti-cytokine agents, etc.);

Translated from Russian to English, dated 26-Nov-2019

- ✓ Systemic medications for psoriasis/psoriatic arthritis, including hydroxyurea, acitretin, cyclosporine, methotrexate, apremilast, fumaric acid derivatives and dimethyl fumarate, intracellular kinase inhibitors, etc., except for NSAIDs;
- ✓ Systemic and intra-articular glucocorticoids;
- ✓ Phototherapy [including selective phototherapy (UVB) and photochemotherapy (PUVA)],
- ✓ Any unauthorized products other than BCD-085;
- ✓ Opioid analgesics;
- ✓ Vaccination with live vaccines.

The study participant who has received or needs any prohibited treatment must be withdrawn from the study.

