8.4. Accounting for missing, unavailable or doubtful data, outliers

Missing, unused, and spurious data will not be substituted.

Spurious and unevaluable data are revealed during the outlier analysis by examination of Mahalanobis or Cook distance, visual analysis of scatter plots and box plots.

All actions taken to handle missing, unevaluable, spurious data and outliers before/during the statistical analysis will be described in the Clinical Study Report.

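### Time to loss of response has no rule for withdrawal caused by worsening psoriasis; censoring such patients by default would understate loss

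*SAP*

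**What the plan says.** Time to loss of PASI 75/90/100, sPGA 0-1 or 0, and DLQI 0-1 is a secondary endpoint of the extension (SAP 4.1; Protocol 7.1.2.3). SAP 8.2 assigns it Kaplan-Meier curves, the log-rank test and a Cox model. The only sentence on censoring, repeated in Protocol 9.1, is: "Right censoring can be used to analyze time to events". Neither document says who is censored, at what date, or how withdrawal is classified.

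Other provisions decide what data exist for a patient who worsens:

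- Protocol 6.2.2: "The study participant who has received or needs any prohibited treatment must be withdrawn from the study". The prohibited list includes "Systemic medications for psoriasis/psoriatic arthritis, including hydroxyurea, acitretin, cyclosporine, methotrexate, apremilast, fumaric acid derivatives and dimethyl fumarate, intracellular kinase inhibitors, etc., except for NSAIDs", as well as biologics and phototherapy.
- Protocol 5.4.1, on dosed patients who leave early: "The Protocol does not specify the amount of procedures to be performed during the Early Withdrawal Visit".
- Protocol, Terms and Definitions, on premature withdrawal: "At this time point, the study therapy stops, and no further assessments are planned". The entry then allows a possible exception for follow-up of survival or disease progression.
- SAP 8.4: "Missing, unused, and spurious data will not be substituted". Protocol 9.6 says the same.
- SAP 9 plans no additional analyses.

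**The concern.** Kaplan-Meier and Cox assume that a censored patient has the same later risk of the event as those who remain. A patient withdrawn because psoriasis has worsened enough to need systemic therapy, a biologic or phototherapy does not meet that assumption. The reason for leaving is the failure that the endpoint is meant to count.

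Loss is seen only when a score is taken. If the patient leaves between scheduled scores and none is taken at withdrawal, the last recorded value is still a response. No event is on file, and the missing-data rule forbids supplying one. What remains is censoring (or exclusion), and either takes a treatment failure out of the event count.

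Maintenance of response is part of the first objective of the extension (Protocol 2.2; SAP 2.2), so the durability estimate is what is at stake. Protocol 8.3.1 also keeps worsening of the main disease out of adverse event reporting, so such a flare need not appear in the safety tables either.

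**Working it through.** **Plan's own figure.** The documents give no expected loss rate, event count or power for this endpoint, so there is nothing to reproduce. The calculation below shows direction and scale only.

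**Inputs from the documents**

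- PASI, sPGA and DLQI are scored at Weeks 62, 74, 86, 98, 110, 122, 134, 146 and 154 in Arms 1 and 2 (Protocol Table 26). That is K = 9 scores, mostly 12 weeks apart.
- The only documented loss rate is 2.6% loss of PASI 75 (n = 77) in the Phase II psoriasis study and its extension, comparing one year with Week 12 (Protocol 1.3.2, extension results).

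**Assumptions (not documented)**

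- L is the true cumulative loss by Week 154, with equal risk in each interval.
- f is the share of losses that end in withdrawal before a failing score and are censored at the previous visit.
- 190 patients enter the extension, used only for the standard error.

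**Formula.** The loss risk per interval is h = 1 − (1 − L)^(1/9). Per patient at risk, f·h leave as censored before the visit and (1 − f)·h are recorded as events among the remaining 1 − f·h. The surviving factor per visit is (1 − h)/(1 − f·h), so

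reported loss = 1 − (1 − L)/(1 − f·h)^9.

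**Worked example, L = 10%, f = 25%.** h = 1 − 0.90^(1/9) = 0.01164 and f·h = 0.00291. Then (1 − 0.00291)^9 = 0.9741, and reported loss = 1 − 0.90/0.9741 = 7.6%.

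| True loss L | f = 0 | f = 25% | f = 50% |
|---|---|---|---|
| 2.6% | 2.6% | 2.0% | 1.3% |
| 5% | 5.0% | 3.8% | 2.5% |
| 10% | 10.0% | 7.6% | 5.1% |
| 20% | 20.0% | 15.5% | 10.6% |

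A simulation with n = 190, exponential loss and 10% unrelated dropout agrees: about 7.7% for L = 10% and 3.8% for L = 5%, both at f = 25%.

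**Scale against sampling error at f = 25%.** SE = √[L(1 − L)/190].

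- L = 2.6%: SE 1.15 points, shift 0.6 points, about half an SE.
- L = 5%: SE 1.58 points, shift 1.2 points, about 0.8 SE.
- L = 10%: SE 2.18 points, shift 2.4 points, about 1.1 SE.

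**Which row is plausible.** The 2.6% covers about 40 weeks (Week 12 to Week 52). If that rate held over the 100 weeks from Week 54 to Week 154, loss would be 1 − 0.974^(100/40) = 6.4%, between the 5% and 10% rows. This is an extrapolation from a two-time-point comparison under mixed doses and regimens, so it is only a rough guide.

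**The case against.** Five points can fairly be made on the other side.

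1. **The SAP does not say that these patients are censored.** It permits right censoring and stops there. A reader might infer that the plan prescribes censoring them as continuing responders; the text does not go that far. This stands. The understatement is what follows by default from the other rules, not a stated method.

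2. **A failing score may be taken at withdrawal.** Protocol 5.4.1 requires an Early Withdrawal Visit on the day of withdrawal unless the patient is lost or cannot attend. Its content is decided case by case, so PASI is neither required nor excluded. Protocol 4.7.9, read literally, has sPGA determined at every visit, although the visit schedule is narrower. Where a failing score is taken, there is no bias for that endpoint. This limits the problem but does not remove it.

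3. **The affected group is narrow.** Losing PASI, sPGA or DLQI response is not a withdrawal criterion in the extension (Protocol 4.8.2 and 5.3). Most patients who lose response stay in and are scored at the next visit. The bias needs a move from response to needing prohibited psoriasis therapy between scores, and departure unscored. A reader might infer that every curve is biased to a similar degree. That is not supported: stricter thresholds such as PASI 100 and sPGA 0 are more likely to be lost at a scheduled visit first.

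4. **Not every such withdrawal concerns psoriasis.** Live vaccines and opioid analgesics are also prohibited, and censoring may be harmless there. The passage on worsening in Protocol 1.5.3, "If the disease worsens and requires additional therapy, the patient can always discontinue the study", was written to justify placebo use, not as an extension rule. Section 6.2.2 carries the argument without it.

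5. **The maintained-response proportions may be unaffected.** A reader might infer that withdrawn patients drop out of those denominators too. The SAP does not define the denominator. Patients could equally stay in it as not maintained.

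**Conclusion.** The concern holds as a conditional one. Under the stated rules, a patient who worsens between scores and is withdrawn without a failing score has no recorded event, and only censoring is on offer. That censoring is informative, and Kaplan-Meier loss is understated roughly in proportion to f. Nothing in either document makes such a withdrawal an event, and no sensitivity analysis would reveal the effect.

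The size is illustrative. At f = 25%, a true 10% would be reported as about 7.6 to 7.7% and a true 5% as about 3.8%. Starting from the documented 2.6%, the shift is about half a standard error. No document fixes f, and f = 0 means no bias.

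The consequence is limited. The endpoint is secondary, in an open-label extension where all arms receive the same regimen. The Week 12 PASI 75 analysis and both study hypotheses are untouched. This is a cheap improvement, worth making while the rule can still be set without knowledge of the withdrawals.

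**What to change.** Add to SAP 8.2, for all time-to-loss endpoints:

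- Withdrawal for worsening of psoriasis or lack of efficacy, or because psoriasis therapy prohibited by Protocol 6.2.2 was received or needed, is a loss of response on the withdrawal date. The patient counts as not maintained at all later weeks.
- Other withdrawals are censored at the last assessment.
- One sensitivity analysis counts every withdrawal as loss.

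This changes the analysis only and leaves the withdrawal rules as they are. It needs no new data: Protocol 4.8.2 already requires the reason for withdrawal to be reported to the sponsor within 24 hours and an Early Withdrawal Form to be completed in the CRF. The cost is a few lines of SAP text and one extra analysis. The downside is that the reported maintenance rate becomes somewhat less favourable.
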